5. ASSESSMENT OF SAFETY

5.1 SAFETY PLAN

5.1.1 Adverse Events of Special Interest for Lebrikizumab

Based on data to date, the theoretical risks associated with IL-13 inhibition, and the risks associated with and for biologic agents in general, *the following* four categories of potential adverse events have been identified as adverse events of special interest for lebrikizumab (refer to the Lebrikizumab IB for more details):

- Local injection-site reactions
- Anaphylactic, anaphylactoid, and hypersensitivity reactions
- Infections
- Malignancies

Collection of information about these events allows for better evaluation and understanding of any potential safety risk to patients (refer to the Lebrikizumab IB for more details).

The documentation and expedited reporting requirements for these adverse events of special interest are described in Section 5.2.2 (reporting of serious events) and Section 5.2.3 (reporting of events of special interest).

The following risk mitigation measures apply to patients receiving the study drug. Adherence to the planned dose regimen of study drug is required unless dosing is held for safety reasons. For study visits at which the study drug dose is withheld because of toxicity, all other study assessments should be performed as per the study schedule.

Recommendations for vigilance with regard to signs and symptoms of particular safety events of interest are summarized in the following sections.

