5.1.1.2 Anaphylactic, Anaphylactoid, and Hypersensitivity Reactions

Anaphylactic, anaphylactoid, and hypersensitivity reactions *to treatment* are considered a potential risk with all biologic medications, including lebrikizumab. *On the basis of newly-available safety data from six studies that were recently unblinded to the study treatment, there were no reports of anaphylaxis per the Sampson's criteria assessed as related to lebrikizumab treatment by an independent external adjudication committee that was blinded to the study treatment. Furthermore, in the study of patients with IPF (Study GB28547, Cohort A) and both atopic dermatitis studies (Study GS29250*

and Study GS29735), there were no reported events of anaphylaxis, anaphylactoid, or serious hypersensitivity reactions meeting search criteria.

Patients with a history of a severe allergic or anaphylactic reaction to a biologic agent or known hypersensitivity to any component of the lebrikizumab injection are excluded from study participation.

Signs of a possible anaphylactic, anaphylactoid, or hypersensitivity reaction include but are not limited to the following:

- Fever, chills, pruritus, urticaria, angioedema, and skin rash
- Cardiopulmonary reactions including chest pain, dyspnea, hypotension, or hypertension
- Persistent gastrointestinal symptoms (e.g., cramping, abdominal pain, vomiting)

Investigators and health care professionals administering lebrikizumab will receive guidance on how to recognize and manage the signs and symptoms of a potential anaphylactic, anaphylactoid, or hypersensitivity reaction and should be familiar with Sampson's criteria for defining anaphylaxis ([Sampson et al. 2006](#); see [Appendix 8](#)). Investigators and health care professionals should also be trained to accurately and appropriately report these events immediately to the Sponsor as adverse events of special interest or as serious adverse events if appropriate (see [Section 5.2](#)).

Health care professionals should also instruct patients on how to recognize the signs and symptoms of any anaphylactic, anaphylactoid, or hypersensitivity reaction and contact a health care provider or seek emergency care in case of any such symptoms. Patients will need to be clinically stable prior to each dose of study drug as assessed by clinical evaluations including vital signs and resting pulse oximetry.

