Patient injections will be administered by a qualified health care professional *or a trained non-health care professional who can legally administer injections*. Patients will be monitored *by a qualified health care professional* for a minimum of 1 hour after dosing for the first three treatment visits and for 30 minutes after dosing for all *subsequent* treatment visits.

If a patient experiences a suspected non-serious hypersensitivity reaction, the case should be discussed with the Medical Monitor prior to continued dosing. If a patient has signs or symptoms of an anaphylactic, anaphylactoid, or serious hypersensitivity reaction, administration of the study drug must be discontinued permanently (refer to [Appendix 8](#) for suggested clinical criteria for diagnosis of anaphylaxis). The patient should be treated according to the standard of care for management of anaphylaxis or an anaphylactoid or hypersensitivity reaction. The patient must discontinue study drug but, whenever possible, should continue to be followed in the study (see [Section 4.6.1.1](#)). A blood sample for measuring total tryptase level should be obtained 1–6 hours after the acute onset of symptoms, whenever possible. The tryptase sample will be collected and

analyzed per the site's local laboratory practice. Blood samples for antibody testing and PK analysis should be obtained at the time of the event whenever possible, and a blood sample for antibody testing should be obtained at the first follow-up visit after the event (e.g., Safety Follow-Up Visit 1; see [Appendix 4](#)).

Detailed information regarding anaphylactic, anaphylactoid, or hypersensitivity reactions that occur during the study will be collected, regardless of whether the events are serious (see Section [5.2.2](#)) or non-serious (see Section [5.2.3](#)).

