5.2.3 Adverse Events of Special Interest (Immediately Reportable to the Sponsor)

Adverse events of special interest are required to be reported by the investigator to the Sponsor immediately (i.e., no more than 24 hours after learning of the event; see Section 5.4.2 for reporting instructions). Adverse events of special interest for this study include the following:

- Adverse events of special interest for general drug development
 - Cases of an elevated ALT or AST in combination with either an elevated bilirubin or clinical jaundice, as defined in Section 5.3.5.6
 - Suspected transmission of an infectious agent by the study drug, as defined below:
 - Any organism, virus, or infectious particle (e.g., prion protein transmitting transmissible spongiform encephalopathy), pathogenic or non-pathogenic, is considered an infectious agent. A transmission of an infectious agent may be suspected from clinical symptoms or laboratory findings indicating an infection in a patient exposed to a medicinal product. This term applies only when a contamination of the study drug is suspected.
- Adverse events of special interest for lebrizumab (see Section 5.1.1 for further information)
 - Local injection-site reactions
 - Anaphylaxis, anaphylactoid and hypersensitivity reactions
 - Infections

Malignancies

- *Adverse events of special interest for pirfenidone*

Elevated liver enzymes (to report cases of elevated ALT or AST in combination with either an elevated bilirubin or clinical jaundice, as defined in Section 5.3.5.6)

Photosensitivity reaction or rash

Gastrointestinal disorders

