3.3.2 Independent Anaphylaxis Adjudication Committee

[figure not shown]
An independent Anaphylaxis Adjudication Committee (iAAC) reviews AEs or groups of AEs that are identified as potential cases of anaphylactic, anaphylactoid, or hypersensitivity reactions. Members of the iAAC are external to the Sponsor and review blinded data to adjudicate cases as anaphylaxis per Sampson's criteria (see [Appendix 7; Sampson et al. 2006](#)).

A detailed description of the procedures and data flow of the AAC is maintained in a separate AAC Charter.

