4.7.2 Adverse Events

Verbatim descriptions of treatment-emergent adverse events (TEAEs) will be coded with use of the latest version of Medical Dictionary for Regulatory Activities (MedDRA) dictionary, and their incidence summarized for each treatment arm by system organ class (SOC) and preferred term. A TEAE is defined as any new AE reported, or any worsening of an existing condition reported on or after the first dose of study drug. In addition, separate summaries will be provided for TESAEs, deaths, and AEs leading to discontinuation of study drug.

Analyses will be performed by treatment group for events of special interest that include anaphylactic reactions, local injection-site reactions, infections, and malignancies.

- Anaphylactic reactions will be reviewed and adjudicated by the iACC.
- Local injection-site reactions will be identified with use of the MedDRA high-level term of “injection site reaction”.
- Infections, as identified with use of the MedDRA SOC of “infections and infestations”.
- Malignancies, as identified on the basis of the Standardized MedDRA Queries (SMQ) of “Malignancy”.

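### SAP 4.7.2 analyses only adjudicated anaphylaxis by arm; the rest of the protocol's hypersensitivity category of special interest has no grouped count

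*Combined protocol and SAP*

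**What the plan says.** **What is collected.** Protocol 5.1.1 lists "Anaphylactic, anaphylactoid, and hypersensitivity reactions" as one of four lebrikizumab categories of special interest. Protocol 5.2.3 repeats it ("Anaphylaxis, anaphylactoid and hypersensitivity reactions") among events the investigator must report within 24 hours. Neither entry is limited to serious events. Protocol 5.1.1.2 states "Detailed information regarding anaphylactic, anaphylactoid, or hypersensitivity reactions that occur during the study will be collected", for serious and non-serious events alike.

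**What is adjudicated.** Under SAP 3.3.2 an external committee receives "potential cases of anaphylactic, anaphylactoid, or hypersensitivity reactions". Its stated task is to "review blinded data to adjudicate cases as anaphylaxis" under Sampson's criteria. No other classification is described; procedures are left to a separate charter.

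**What is analysed.** SAP 4.7.2 plans by-group analyses of "events of special interest that include anaphylactic reactions, local injection-site reactions, infections, and malignancies". For the first category the only definition is: "Anaphylactic reactions will be reviewed and adjudicated by the iACC". The other three each have a MedDRA grouping: a high-level term for injection-site reactions, a system organ class for infections and a standardised query for malignancies. Protocol 6.5.1 has the same four categories and also relies on adjudication for the first. SAP 1 says that the SAP's analysis plan supersedes the protocol's.

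**What else is tabulated.** SAP 4.7.2 summarises all treatment-emergent events for each arm by system organ class and preferred term. Serious events, deaths and events leading to discontinuation of study drug have their own summaries.

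**The concern.** The category is wide at collection and narrow at analysis. A case of urticaria or angioedema that is referred to the committee and judged not to be anaphylaxis belongs to the protocol's category of special interest, but it has no place in the analysis written for that category. It appears only under its own preferred term.

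For rare, related reactions, reading term by term is a weak way to find a difference. The signs named in protocol 5.1.1.2, such as pruritus, urticaria, angioedema and rash, are coded separately, so each row may hold only a few patients. If a grouping is chosen only after the arms are known, it is post hoc and carries less weight. SAP 1 says the study was re-designed to support registration and labelling, so a reader of the safety section will look for this category.

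**Working it through.** The point is textual, and the plan states no figure for it to reproduce. The arithmetic gauges two things: how much the adjudicated row is likely to contain, and how much visibility is lost by splitting. SAP 4.7 describes the safety output as summaries, so power is used here only as a measure of visibility.

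**1. The category followed through the documents**

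| Step | Scope | Source |
|---|---|---|
| Reporting | anaphylactic, anaphylactoid, hypersensitivity | Protocol 5.1.1, 5.2.3 |
| Detail collected | same, serious or not | Protocol 5.1.1.2 |
| Referral to committee | same | SAP 3.3.2 |
| Committee decision | anaphylaxis | SAP 3.3.2 |
| Special-interest analysis | adjudicated anaphylactic reactions | SAP 4.7.2, protocol 6.5.1 |

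The narrowing occurs at the committee decision, and no later step brings back the other cases as a group.

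**2. Likely content of the adjudicated row**

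Protocol 5.1.1.2 reports no anaphylactic, anaphylactoid or serious hypersensitivity event meeting search criteria in Cohort A, where 78 patients received lebrikizumab (protocol 5.1.1.1). For 0 of 78, the one-sided 95% upper bound is 1 − 0.05^(1/78) = 3.8%.

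The planned Cohort B arm is 165 patients (SAP 2.3). With an assumed anaphylaxis rate p, the expected count is 165p and the chance of no case is (1 − p)^165:

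| Assumed p | Expected cases | Chance of none |
|---|---|---|
| 0.1% | 0.17 | 85% |
| 0.2% | 0.33 | 72% |
| 0.5% | 0.83 | 44% |
| 1% | 1.65 | 19% |

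Over this range the row would be expected to hold fewer than two cases. It is likely to contain few or none, but it is not certain to be empty.

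**3. What splitting costs**

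The documents give no hypersensitivity rate, so all rates below are assumed. With 165 per arm, the table gives exact power of a two-sided Fisher test at 0.05, first for one grouped count. It then gives power for a given single term when each affected patient has one term and the events divide evenly over four. The last column, 1 − (1 − single-term power)^4, is the chance that at least one of the four terms reaches 0.05, treating them as independent.

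| Assumed rates | Expected patients | Grouped | Given single term | Any of four |
|---|---|---|---|---|
| 4% vs 1% | 6.6 vs 1.7 | 27% | 0.4% | 2% |
| 6% vs 2% | 9.9 vs 3.3 | 35% | 2% | 7% |
| 8% vs 2% | 13.2 vs 3.3 | 64% | 6% | 21% |
| 10% vs 3% | 16.5 vs 5.0 | 68% | 9% | 31% |

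In the third row, 1 − (1 − 0.057)^4 = 21%. A grouped difference of 13.2 against 3.3 patients becomes four rows of about 3.3 against 0.8.

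**The case against.** **The events are in the tables.** This stands. A reader might infer that hypersensitivity short of anaphylaxis will not be compared between arms, or that most of the category is thrown away. The documents do not support that. Every treatment-emergent event is tabulated by arm and preferred term. Serious reactions also enter the serious-event table and, because protocol 4.6.1.1 requires study drug to stop for them, the discontinuation table. What is missing is a grouped count, and it matters most for non-serious events that do not stop treatment.

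**This is not simply protocol against SAP.** This also stands. Protocol 6.5.1 narrows the category in the same way, so the SAP follows the protocol's own analysis section. The mismatch is between the reporting sections and the analysis sections.

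**The row may not be empty, and an empty row is no fault.** A reader might take the six-study statement beginning "there were no reports of anaphylaxis per the" as showing that the adjudicated row must be empty. It does not: that statement covers only cases judged related to lebrikizumab, and the planned row has no such limit. A count of zero adjudicated cases is also useful information. The complaint is that nothing stands beside it.

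**The list is open, and search criteria exist.** SAP 4.7.2 uses the word include, and the committee charter may hold more detail. The Cohort A account in protocol 5.1.1.2 also refers to search criteria that reach serious hypersensitivity. But the SAP states no criteria, so nothing in it ensures that Cohort B is reported on the same basis or that non-serious events are grouped.

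**Pirfenidone adds skin events.** All Cohort B patients take it, and protocol 5.1.4.2 gives photosensitivity in 9% of pirfenidone patients against 1% on placebo. A grouping that includes rash could dilute a difference. This stands and shapes the fix.

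**Other safeguards.** The independent monitoring committee reviews unblinded safety data about every 6 months. That protects patients during the trial, but it does not settle how the final report presents the category.

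**Conclusion.** The gap is real and moderate. A category that the protocol singles out for urgent reporting is analysed as a group only for its adjudicated anaphylaxis, a row likely to hold few or no cases. Other hypersensitivity is visible by arm only as separate preferred terms, plus the serious and discontinuation tables where those apply. It is also the only one of the four lebrikizumab categories without a MedDRA grouping.

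The mismatch rests on the text alone. Its practical size rests on assumed rates and an assumed even split over four terms: at 8% versus 2%, visibility falls from 64% for one grouped count to 6% for a given term, or 21% for any of the four. Less even splitting would shrink that loss. The primary analysis, its error rate and the conduct of the trial are not affected. The change is worth making before Cohort B is unblinded, because a grouping fixed then is not open to the charge of being chosen after the result.

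**What to change.** Add one bullet to SAP 4.7.2, and align protocol 6.5.1 if the protocol is amended again. For each cohort, by arm and over the periods already set in SAP 4.7:

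- The number and percentage of patients with a hypersensitivity event by a pre-specified MedDRA grouping, for example the Hypersensitivity standardised query (narrow), with the MedDRA version stated. Show it with and without rash and photosensitivity terms, because of the pirfenidone background in Cohort B.
- All cases sent to the adjudication committee, with the outcome (anaphylaxis or not).
- In both tables, flag serious events and those leading to discontinuation of study drug.

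Keep the adjudicated anaphylaxis row as planned. Cohort A was unblinded in May 2016 (protocol 1.4), so label its grouped row as added after unblinding.

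The cost is one bullet and a few descriptive tables from data already collected. There is no change to design, sample size, testing or clinical management. The remaining downside is background skin events in both arms, which the paired presentation makes visible.

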4.7.3 Laboratory Data

Serum chemistry and hematology, evaluations will be summarized by descriptive statistics for each treatment group, together with changes from baseline (Visit 2 value). In addition, all chemistry, hematology, urinalysis, and coagulation data outside the normal reference ranges will be tabulated in terms of the number and proportion of patients with values that are out of range. The toxicity grade at baseline and the highest toxicity grade during the placebo-controlled treatment phase for select labs (eosinophils absolute count, hemoglobin, WBC, platelets, alanine aminotransferase, aspartate aminotransferase, bilirubin, creatine kinase) will be summarized by treatment group.

The number and percentage of patients with positive serum antibodies at baseline and during the study will be tabulated.

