5.3.5.4 Abnormal Laboratory Values

Not every laboratory abnormality qualifies as an adverse event. A laboratory test result should be reported as an adverse event whether it meets any of the following criteria:

- Accompanied by clinical symptoms
- Results in a change in study treatment (e.g., dosage modification, treatment interruption, or treatment discontinuation)
- Results in a medical intervention (e.g., potassium supplementation for hypokalemia) or a change in concomitant therapy
- Clinically significant in the investigator’s judgment

It is the investigator’s responsibility to review all laboratory findings. Medical and scientific judgment should be exercised in deciding whether an isolated laboratory abnormality should be classified as an adverse event.

If a clinically significant laboratory abnormality is a sign of a disease or syndrome (e.g., alkaline phosphatase and bilirubin five times the upper limit of normal [ULN] associated with cholecystitis), only the diagnosis (i.e., cholecystitis) should be recorded on the Adverse Event eCRF.

If a clinically significant laboratory abnormality is not a sign of a disease or syndrome, the abnormality itself should be recorded on the Adverse Event eCRF, along with a descriptor indicating whether the test result is above or below the normal range (e.g., “elevated potassium,” as opposed to “abnormal potassium”). If the laboratory abnormality can be characterized by a precise clinical term per standard definitions, the clinical term should be recorded as the adverse event. For example, an elevated serum potassium level of 7.0 mEq/L should be recorded as “hyperkalemia”.

Observations of the same clinically significant laboratory abnormality from visit to visit should not be repeatedly recorded on the Adverse Event eCRF, unless the etiology changes. The initial severity of the event should be recorded, and the severity or

seriousness should be updated any time the event worsens (see Section 5.3.5.3 for details on recording persistent adverse events).

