6.5.3 Laboratory Tests

Descriptive summaries of laboratory values at baseline and throughout the study will be generated and listed on the basis of a graded scale for selected parameters. For these selected parameters, changes from baseline and the proportion of patients experiencing clinically significant changes relative to baseline will be summarized by treatment arm.

The number and percentage of patients with positive serum antibodies to lebrikizumab at baseline and during the study will be tabulated.

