4.1 Analysis Populations	14
4.1.1 Intent-to-Treat Population.....	14
4.1.2 Per Protocol Population	14
4.1.3 Pharmacokinetic-Evaluable Population	14
4.1.4 Safety Population	14
4.2 Analysis of Study Conduct.....	15
4.3 Analysis of Treatment Group Comparability	15
4.4 Efficacy Analysis.....	15
4.4.1 Type I Error Control Plan.....	15

4.4.2	Primary Efficacy Endpoint.....	16
4.4.3	Secondary Efficacy Endpoints.....	17
4.4.4	Exploratory Efficacy Endpoints.....	19
4.4.5	Sensitivity Analyses.....	19
4.4.6	Subgroup Analyses.....	20
4.5	Pharmacokinetic Analyses.....	22
4.6	Biomarker Analyses.....	22
4.6.1	Pharmacodynamic Biomarker Analyses.....	22
4.7	Safety Analyses.....	22
4.7.1	Exposure of Study Drug.....	23
4.7.2	Adverse Events.....	23
4.7.3	Laboratory Data.....	23
4.7.4	Vital Signs.....	23
4.7.5	ECG Results.....	24
4.8	Missing Data.....	24
4.9	Interim Analyses.....	24
5.	REFERENCES.....	25

LIST OF TABLES

Table 1	Subpopulation Definitions.....	21
---------	--------------------------------	----

LIST OF FIGURES

Figure 1	Cohort A Study Schematic.....	7
Figure 2	Cohort B Study Schematic.....	8

LIST OF APPENDICES

Appendix 1	Protocol Synopsis.....	26
Appendix 2	Schedule of Assessments: Screening and Placebo Controlled Treatment Period - Cohort A.....	34
Appendix 3	Schedule of Assessments: Open-Label Lebrikizumab Treatment Period - Cohort A.....	39
Appendix 4	Schedule of Assessments: Screening, Pirfenidone Titration Run-In, and Placebo-Controlled Treatment Period - Cohort B....	43
Appendix 5	Schedule of Assessments: Safety Follow-Up Period.....	49

Appendix 6	GAP Index and Staging System for IPF.....	52
Appendix 7	Clinical Criteria for Diagnosing Anaphylaxis.....	53

1. **BACKGROUND**

This statistical analysis plan (SAP) provides details on the study design, outcome measures, and statistical analysis plan for Study GB28547. The outcome measures and the statistical analysis plan in this SAP supersede those specified in the protocol. The SAP was finalized prior to Cohort A unblinding and is currently being amended prior to unblinding Cohort B.

[REDACTED] Since then, two agents have been approved for the treatment of idiopathic pulmonary fibrosis (IPF) (Esbriet[®] [pirfenidone], Ofev[®] [nintedanib]), and Study GB28547 has been re-designed to support registration and labeling. Key changes to study design since 2013 have included:

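### For all but the eight graded routine laboratory tests, the SAP's only categorical table is an out-of-range count with no baseline condition, direction or stated window, which dilutes new abnormalities

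*Combined protocol and SAP*

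**What the plan says.** SAP 4.7.3 plans four laboratory summaries.

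- Serum chemistry and hematology get descriptive statistics by arm, with change from the Visit 2 value.
- For a wider set, "all chemistry, hematology, urinalysis, and coagulation data outside the normal reference ranges will be tabulated in terms of the number and proportion of patients" with such values.
- "The toxicity grade at baseline and the highest toxicity grade during the placebo-controlled treatment phase for select labs" are summarized by arm. The select labs are "eosinophils absolute count, hemoglobin, WBC, platelets, alanine aminotransferase, aspartate aminotransferase, bilirubin, creatine kinase".
- For antibodies, "The number and percentage of patients with positive serum antibodies at baseline and during the study will be tabulated".

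Protocol 6.5.3 has a baseline-referenced categorical summary, in which "changes from baseline and the proportion of patients experiencing clinically significant changes relative to baseline will be summarized by treatment arm". It applies only to selected parameters that the protocol does not name. SAP Section 1 adds: "The outcome measures and the statistical analysis plan in this SAP supersede those specified in the protocol".

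SAP 4.7 sets the general period for safety summaries. It is the placebo-controlled period, plus safety follow-up for Cohort B and for Cohort A patients who do not enter the extension; the Cohort A open-label period is summarized separately. The out-of-range sentence in 4.7.3 names no period of its own, whereas the grade summary is tied to the placebo-controlled phase.

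**The concern.** A safety reader wants to know who became abnormal on study drug. The out-of-range count does not ask that. Nothing in the sentence excludes a patient who was already out of range at Visit 2, and nothing separates high from low values. Limiting the count to post-baseline draws would not be enough, because a patient abnormal at Visit 2 who stays abnormal would still be counted.

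The neighboring sections do better. SAP 4.7.2 limits treatment-emergent adverse events to new or worsening ones, SAP 4.7.5 names ECG changes that are new on treatment, and the antibody table separates baseline from on-study status.

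Such patients can enter the trial. The only numeric laboratory entry limits are on AST, ALT and total bilirubin (Protocol 4.1.2) and, in Cohort B, creatinine clearance (Protocol 4.1.2.1). Other abnormalities are left to the investigator's judgment. At stake is how easily a real laboratory effect can be seen in the categorical tables for the ungraded tests.

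**Working it through.** The documents state no figure for these tables, so there is nothing to reproduce. The check has two parts: what each group of tests receives, and how much dilution follows under stated assumptions.

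**Coverage (SAP 4.7.3 against the laboratory list in Protocol 4.5.14)**

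| Data | Change from baseline by arm | Baseline-referenced categories | Out-of-range count |
|---|---|---|---|
| Eight graded tests | yes | yes | yes |
| Other chemistry and hematology | yes | no | yes |
| Urinalysis | no | no | yes |
| Antibodies | no | yes (positivity) | no |
| Coagulation | no | no | named, but never collected |

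Protocol 4.5.14 lists 20 chemistry items (total and direct bilirubin counted separately), 12 hematology items and 7 urinalysis items: 20 + 12 + 7 = 39. If the graded bilirubin means one of the two, 39 − 8 = 31 items have the out-of-range count as their only categorical laboratory table. Coagulation is absent from that list and from the schedules of assessments.

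**Dilution (assumed rates)**

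Let b be the share out of range at baseline, equal in the two arms in expectation by randomization, and let p be the risk of a new abnormality among the rest. If all baseline-abnormal patients are counted, the table shows

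observed rate = b + (1 − b)p.

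The between-arm difference is (1 − b)(p1 − p0). It is zero whenever p1 = p0, so no false difference is created. A real difference shrinks by the factor (1 − b), and the ratio shrinks faster.

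With p assumed to be 15% versus 5% (true ratio 3.0):

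- b = 10%: 0.10 + 0.90 × 0.15 = 23.5%; 0.10 + 0.90 × 0.05 = 14.5%; ratio 1.62.
- b = 30%: 0.30 + 0.70 × 0.15 = 40.5%; 0.30 + 0.70 × 0.05 = 33.5%; ratio 1.21.
- b = 50%: 0.50 + 0.50 × 0.15 = 57.5%; 0.50 + 0.50 × 0.05 = 52.5%; ratio 1.10.

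With p assumed to be 20% versus 10% (true ratio 2.0):

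- b = 20%: 36% versus 28%; ratio 1.29.
- b = 30%: 44% versus 37%; ratio 1.19.
- b = 40%: 52% versus 46%; ratio 1.13.

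**Sensitivity on a power scale**

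No test is planned on these tables, so this only gauges how visible a difference would be. Inputs are the 15% versus 5% case and 165 patients per arm (Cohort B, SAP 2.3). The power is that of a two-sided 5% comparison of two proportions, Φ[(d − 1.96·se0)/se1], where d is the absolute difference between the two proportions and se0 and se1 are the pooled and unpooled standard errors. The restricted analysis uses 165(1 − b) patients per arm.

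| b | All patients counted | Only patients normal at baseline |
|---|---|---|
| 0% | 0.86 | 0.86 |
| 10% | 0.55 | 0.82 |
| 30% | 0.26 | 0.72 |
| 50% | 0.15 | 0.57 |

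The two tables coincide when nobody is abnormal at entry. If some baseline-abnormal patients normalize and only post-baseline values count, the dilution is smaller than shown.

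**The case against.** A reader might infer that on-treatment laboratory changes will be swamped. The documents do not support that.

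- The SAP is silent on baseline-abnormal patients and on direction. Counting everyone is the literal reading, not a stated rule.
- Chemistry and hematology also get change from baseline by arm, so a shift in creatinine, for example, has another place to appear.
- Protocol 5.3.5.4 sends relevant abnormalities to the adverse event tables: "A laboratory test result should be reported as an adverse event whether it meets any of the following criteria", namely symptoms, a change in study treatment, a medical intervention or change in concomitant therapy, or clinical significance. SAP 4.7.2 then summarizes new or worsening events. The independent Data Monitoring Committee also reviews unblinded safety data about every 6 months.
- The graded list includes the liver tests and eosinophils, to which the documents give particular attention.

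This stands, with gaps. Mean changes can miss large shifts in a few patients. Urinalysis has no change-from-baseline summary. Investigators are blinded to monocyte values after randomization (Protocol 4.5.14), so their own review cannot turn a monocyte result into an adverse event; an external Medical Monitor sees the values, but monocytes are not graded.

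A second tempting argument is chance excursions over repeated draws. Chemistry is drawn at 7 scheduled post-baseline visits in Cohort A and 10 in Cohort B, or 9 and 12 with the two later safety follow-up visits. For independent draws and a 95% reference range, 1 − 0.95^9 = 37% and 1 − 0.95^12 = 46% of patients would be out of range at least once. Patients normal at Visit 2 would have the same excursions, so this is no argument for a treatment-emergent table.

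Finally, counting only patients normal at baseline would hide worsening in those already abnormal. That is a fair criticism of a simple replacement, and it is why the remedy below is a shift table.

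**Conclusion.** The point holds as a cheap improvement to descriptive safety tables, not as a threat to the trial's conclusions. Exactly eight tests receive baseline and worst grades. The other routine chemistry, hematology and urinalysis tests have one categorical laboratory table, and as written it does not separate new from pre-existing abnormality or high from low.

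The consequence is dilution without bias. Its size cannot be computed from the documents, because they give no baseline abnormality rates. Under the assumed rates, dilution is moderate for tests seldom abnormal at entry (3.0 to 1.62 at 10%) and severe only for tests often abnormal at entry (3.0 to 1.10 at 50%). These figures also assume that every baseline-abnormal patient is counted. Urinalysis is the least protected. Naming coagulation is a plain error.

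**What to change.** In SAP 4.7.3, replace the out-of-range sentence with the following.

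- For each test and direction (high, low), present by arm a shift table from Visit 2 to the worst post-baseline value. Include the number and proportion of patients not out of range in that direction at Visit 2 who become so after the first dose, with those at risk as denominator.
- For urinalysis, show negative at baseline to positive after the first dose.
- Keep patients already abnormal at baseline as separate rows, and retain the chemistry and hematology change-from-baseline summaries so that worsening among them stays visible.
- State the period covered, consistent with SAP 4.7.
- Delete coagulation.

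The cost is SAP wording and a standard program; all values are already collected. The downsides are denominators that differ by test and more table rows. SAP Section 1 places the current amendment before Cohort B unblinding, so the change can be made for Cohort B while the treatment codes are still closed. The Cohort A placebo-controlled analysis has already been run, so there it would be an additional output.
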